6.4 Outcomes

Assessment: The following tests will be administered as baseline and post-intervention. Table 1: Assessment variables for Groups 1 and 2 (In-person assessment) and Group 3 (Online-assessment)

| Group 1 and 2 Assessments (In-person assessment) | Group 3 Assessments (Online Assessment) | | | | | | |
|--|---|--|--|--|--|--|--|
| Balance Intentional balance control (Limits of stability test) (single and Dual task conditions) Postural control (sensory organization test) (single and Dual task conditions) Reactive balance control (Stance perturbation test) (single and Dual task conditions) NIH balance Toolbox (Standing balance test) Gait GaitRite mat (single and Dual task conditions) NIH Balance toolbox (4m walk Gait speed test) | Balance - 30-second chair stand test - Four-step square test - Sharpened Romberg's - One leg stance test Gait - Tinetti Performance Oriented Mobility Assessment | | | | | | |
| Muscular fitness - Isokinetic Dynamometer - B-mode Ultrasonography Cardiovascular fitness - Heart rate variability - YMCA submaximal cycle Ergometer test - NIH Balance toolbox (2-minute walk endurance test) | Cardiovascular fitness - 2-minute step in place test | | | | | | |
| Cognitive performance - Neuropsychological battery tests - NIH cognitive toolbox - Auditory clock test and letter number sequencing (single and Dual task conditions) Physical activity and motivation - Smartphone (Android/iphone) | Cognitive performance - Neuropsychological battery tests - NIH cognitive toolbox - Auditory clock test and letter number sequencing (single and Dual task conditions) Physical activity and motivation - Smartphone (Android/iphone) | | | | | | |

| fMRI scanning | - |
|---|---|
| - Intrinsic motivational index | - Intrinsic motivational index |
| - Physical activity scale for the elderly | - Physical activity scale for the elderly |
| - Quality of life (SF-36) | - Quality of life (SF-36) |
| - Wearable sensor | - Wearable sensor |
| | |

Aim 1: Balance and Gait tests:

Balance:

For In-Person Assessment (Group 1 and 2)

Intentional balance control

Intentional postural sway will be examined via the Limits of Stability test protocol (Single task - ST) on the Balance Master (National Instruments etc.) and will also be examined while concurrently performing an oral trail making task, i.e. letter-number sequencing (dual-task condition, dual - DT) and /or Auditory Clock Test. The Equitest is a special equipment consisting of metal frame embedding forceplates with a surrounding visual display. Participants will be in a harness for their safety in case they get unsteady during any of the conditions inducing a sensory conflict. This will take about 15 minutes.

Postural Control

Sensory organization test will be administered using the Equitest equipment. This test quantitatively assesses the participant's ability to use visual, proprioceptive and vestibular inputs for maintaining their posture in quiet standing. The test will be administered under single and dual-task (simultaneous performance of motor and cognitive tasks) conditions. The test will take approximately 10 minutes to complete. Participants will be in a harness for their safety in case they get unsteady during any of the conditions inducing a sensory conflict.

Reactive balance control

Reactive balance control will be examined via the stance perturbation test under single and dual-task conditions (simultaneous performance of letter number sequencing task or auditory clock task). The participant will be prepared with 29 Helen-Hayes passive reflective markers placed on several joints on the body (knee joint, ankle joint, wrist, shoulder, hip, sacrum, neck). The participant will be in a harness and instructed to stand shoulder width apart on the Active Step Treadmill making sure both his feet are on the treadmill belt. The harness provides support making sure the participants knee do not land on the treadmill surface and avoid injury. A 3-D motion captures cameras will be used to capture the body kinematics and cortex software for collecting the data will be used. Prior to the experiment, the participant will be educated about what will he be experiencing once the test starts and will be instructed to respond naturally when an

unexpected perturbation occurs. After the participant attains a comfortable stance position on the treadmill belt, a sudden unannounced slip-like or trip-like perturbation will be induced, and their responses will be recorded. During the dual-task condition, the participant will be provided with the cognitive task at the beginning and any time after the participant begins to respond to the cognitive task, a slip-like or trip-like perturbation will be induced to the participant. Another research personnel will always guard the participant during the test as a safety precaution.

For analysis purpose, their kinematic data will be run through a customized MATLAB code for computing the required variables for analysis.

NIH balance toolbox

Locomotion and Balance measures of the NIH Balance toolbox will be used to assess their clinical balance scores via the NIH toolbox application using the iPad and iPod. The locomotion test involves 4-meter walk gait speed test. The total time taken to complete the 4-meter walk will be noted on the iPad. This test will take about 3 minutes to complete the task. The standing balance test involves maintaining stance position without losing balance at five different positions (eyes open on a solid surface, eyes closed on a solid surface, eyes open on a foam surface, eyes closed on a foam surface, eyes open in tandem stance position on a solid surface). The iPod will be clipped on the gait belt which will be buckled around the participants' waist. This test will take 7 minutes to complete the tasks. The participant will wear a gait belt throughout and a research personnel will be around to provide contact guard support during this test. Two-minute walk test will be conducted on a 60 feet walkway. In this test, the participant will be asked to walk up and down the 60 feet walkway for two minutes. The total distance covered will be recorded in a chart provided by the application on the iPad.

For Online Assessment (Group 3)

[figure not shown]
Balance will be determined with the following tests:

1) 30-second chair stand test. This test is conducted to assess leg strength and endurance. Participants will be asked to stand in front of a sturdy chair and monitored by the remote research personnel during the test. The participants will be instructed to sit in the middle of the chair. Place their hands on the opposite shoulder crossed, at the wrists. Keep their feet flat on the floor and back straight with arms against their chest. Then the following instruction "On "Go," rise to a full

standing position, then sit back down again. 6. Repeat this for 30 seconds" is provided to conduct the test and assessed by the research personnel remotely. This test is easy to perform and requires a sturdy chair (available at every home) and will be performed in front of the camera during the zoom meeting for the research personnel to monitor and collect the required data.

- 2) To test the dynamic balance and to assess the person's ability to step over objects forward, sideways, and backwards, a **Four-step square test** will be used. The participants will be instructed to stand in square 1 facing square 2 (see fig below). The
 - participants are instructed to step as fast as possible into each square in the following sequence: 2,3,4,1,4,3,2, and 1 and required them to step forward, backward, and sideways to the right and left. Participants will be provided with the following instruction "Try to complete the sequence as fast as possible without touching the sticks. Both feet must contact the floor in each square. If possible, face forward during the entire sequence." The research

- personnel will instruct and monitor the participants remotely and note the time the participants took to complete four-step square test. This requires a removable tape to be pasted on the floor (which will be mailed in case they do not have a tape at home). The test is easy to be performed by individuals and does not require any other special equipment to measure their performance.
- 3) To assess the static balance of participants in sensory integration taxing condition, they will be assessed on **Sharpened Romberg** (27,28). Participants will be shown on the screen the positions they need to stand in and will be assessed by the remote research personnel. Further the participants will also be assessed on **One-legged Stance test** to assess static postural and balance control (27,29). Participants will be instructed the following" Stand on one leg, place your arms across your chest with your hands touching your shoulders and do not let your legs touch each other. Look straight ahead with your eyes open and focus on an object about 3 feet in front of you. Ideally do this with the shoes off." Remote research personnel will assess the performance of the participant. This test does not require any equipment and is safe to administer remotely.

All these tests will be performed on single and dual task conditions. Under dual-task conditions, concurrently performed with an oral trail making task, i.e., letter-number sequencing (dual-task condition, dual - DT) and/or Auditory Clock test. The participants will be asked to place a sturdy chair in front of them for their safety in case they get unsteady during any of the above tests.

Gait function

For In-person Assessment (Groups 1 and 2)

Subjects will be asked to walk on the GAITRite, an electronic mat (CIR Systems, Inc., Sparta, NJ, USA). It consists of sensors embedded into 12 × 2 feet mat which measures spatial and temporal gait parameters via the accompanying GaitRite software (GaitRite Gold, Version 3.2). Dual-task performance will also be performed while walking.

For Online Assessment (Group 3)

Gait assessment (walking stance, walking pattern, step symmetry, trunk) of **Tinetti Performance Oriented Mobility Assessment** will be evaluated remotely to assess gait problems in older adults (30,31). A safe area visible to the research personnel remotely will be chosen and only then the test will be administered. During this test, the research personnel will ensure that he/she is constantly visible in the screen and measure the time taken to complete the test

Muscular Fitness

For In-Person Assessment (Groups 1 and 2)

Participants will be tested for lower extremity muscle strength and muscle size using isokinetic dynamometer. The Peak muscle torque/power generated by biodex software and Muscle cross sectional area will be examined.

Muscle cross-sectional area: For this, the participant will be asked to stand in a comfortable relaxed position. The midpoint of thigh will be marked for measuring the muscle thickness of quadriceps femoris. B-mode Ultrasonography via Sonosite M Turbo machine will be used to measure this muscle thickness with a 5 Hz scanning head. The scanning head will be pretreated with water-soluble transmission gel to provide contact on the marked surfaces without compressing the skin surface. Then, the transducer head will be positioned perpendicular to the longitudinal axis of the quadriceps for which the machine will provide with ultrasound images and electric calipers will be used for noting the muscle thickness.

Cardiovascular exercise tolerance

For In-Person Assessment (Groups 1 and 2)

Participants' Heart rate variability will be tested during all laboratory measures using the Polar ProTrainer 5 RS 800CX GPS. We would compare the change in indexes of heart rate variability over the period of training.

YMCA submaximal cycle Ergometer test: Prior to testing, the participants will be asked to notify the research personnel if they experience any discomfort such as nausea, dizziness during testing. The participants will pedal on the cycle ergometer for 1 minute as a warm-up without resistance at a rate of 50 revolutions per minute (rpm). The participant will continue to pedal at 50 rpm with increased resistance (25 Watts- Fist workload). We will record the heart rate at 2 and 3 minutes. If the difference between the heart rate at 2nd and 3rd minute are greater than 5, the participant will continue for another minute and we will then record the heart rate at 4 minutes. Based on the steady-state heart rate (HR) reached, we will increase the workload for the second stage or workloads beyond the fourth stage and/or increase the intensity by 25 watts (0.5 Kp) until the termination heart rate is reached (85% of age predicted max). The participant will cool down after the last stage has been completed.

For Online Assessment (Group 3)

2-minute step in place test: The participant is asked to stand up straight next to the wall while a mark is placed on the wall at the level corresponding to midway between the kneecap and top of the hip bone. The subject then marches in place for two minutes, lifting the knees to the height of the mark on the wall. Resting is allowed and holding onto the wall or a stable chair is allowed. Stop after two minutes of stepping. The remote research personnel records the total number of times the right knee reaches the tape level in two minutes.

Cognitive Function

For In-Person Assessments (Groups 1 and 2)

- 1) Neuropsychological battery of tests: This will be administered using DirectRT software [34] which has been validated and is a reliable tool to determine cognitive functioning. The participant will be provided with a pair of headphones with an attached microphone for his responses to be audio recorded. A keyboard and mouse will be provided for use during the games as required. 1) Visual Stroop test is a demonstration of interference in the reaction time of a task. In this test, the participant will be asked to read the ink color in which the word is printed and not read the word. 2) Category Fluency Task: This task assesses semantic fluency and requires the participant to recite as many words he can pertained to the category heard, e.g., animals, boys' names, and fruits in one minute. 3) Verbal Fluency Task: In this test, the participant will be asked to recite as many words as possible from the letter cue heard, e.g., "A". 4) Reaction time task: The participant will be asked to hit a number on the keypad corresponding to the position of the yellow dot on the screen. 5) Paired Associated Learning: In this task, the participant is instructed to observe numbers with their positions on the grid which will appear for only a few seconds, and when the cue, i.e., a specific number from the grid is given, the participant is expected to respond to the position the number was on the grid he observed. 6) Spatial Working Memory: The participant is asked to use the mouse to click on the red boxes to find a star. He will be instructed to avoid clicking on the boxes he already found the star in and find the stars in all the boxes for the game to progress. The game consists of 3 levels and the level progresses with the level of difficulty. The game will not progress if he does not complete that level given. 7) Auditory stroop task: The participant will hear words "High" and "Low" at high or low pitches. His/her task is to respond to the pitch of the word and not repeat the word. The responses will be audio recorded.
- 2) NIH cognitive toolbox [35,36,37] measures will be used to determine the change in the cognitive function. It is a standardized test widely used which is highly reliable and valid to use among the mild cognitively impaired older adults administered via the iPad using the NIH Toolbox application. All the responses will be recorded by the iPad and

scores will be generated accordingly which can then be exported via excel sheet. 1) Picture sequence memory test: This test evaluates the episodic memory of the individual. The participant recalls a series of pictures in a particular manner described before. For example, the participant is shown pictures about how to go camping. A series of pictures are shown on building a tent to fishing. For the test, the pictures are jumbled, and the participant is expected to place those pictures in the same order described. The number of adjacent pairs of pictures placed correctly will score a point. The scores are application generated. 2) Flanker inhibitory control and attention test: In this test, the individual is instructed to click on the arrow on the keyboard that matches the direction of the middle arrow in the stimulus given on the screen. Accuracy of the responses are recorded, and the scores are application generated. 3) List Sorting Memory test: The test is divided into two subsets to evaluate working memory. The participant will be shown a picture of animals. For the first subset, the task for the participant is to name the animals from smallest size to the largest size. The second subset involves a category of food along with pictures of animals. The task of the participant is to say the food first and then name the animals from smallest size to the largest size. The accuracy of the participants' response will be recorded by the application. 4) Dimensional Change card sort: This test involves three subsets assessing executive functioning. For the first subset, the participant is expected to choose the same shape of the stimulus provided, for example, if the stimulus given is a boat, and for the answers from which the participant is supposed to choose is given as rabbit and boat, he is expected to click on the boat. In the second subset, the participant is expected to click on the object that matches the color of the stimulus and avoid clicking on the same shape. The last subset involves playing the first and the second subset together in a randomized order generated by the application. 5) Pattern comparison Processing speed test: This test involves the participant to hit the yes or no button depending on the pictures provided look the same or not. Similarity of shapes of objects, colors are provided as stimulus. This test evaluates the processing speed of cognitive functioning.

3) Auditory Clock test: The participant will hear times of day. His/her task is responding yes if both the hour and minute hands are on the same side of the clock face and respond no if the hands are not on the same side of the clock face. The responses will be audio recorded.

4) Letter number sequencing:

For Online Assessment (Group 3)

For all the cognitive tests, the research personnel will share his/her screen to input the cues. The responses will be recorded and saved for data analyses. **Visual Stroop**-

Visual Stroop test is a demonstration of interference in the reaction time of a task. In this test, the participant will be asked to read the ink color in which the word is printed and not read the word. Auditory Stroop- The participant will hear words "High" and "Low" at high or low pitches. His/her task is to respond to the pitch of the word and not repeat the word. The responses will be audio recorded. Flanker inhibitory control and attention test- In this test, the participant is instructed to verbally respond right or left that matches the direction of the middle arrow in the stimulus given on the screen. Accuracy of the responses are recorded. List Sorting Memory test- The test is divided into two subsets to evaluate working memory. The participant will be shown a picture of animals. For the first subset, the task for the participant is to name the animals from smallest size to the largest size. The second subset involves a category of food along with pictures of animals. The task of the participant is to say the food first and then name the animals from smallest size to the largest size. The accuracy of the participant's response will be audio recorded. **Dimensional Change card sort**- This test involves three subsets assessing executive functioning. For the first subset, the participant is expected to say the same shape of the stimulus provided, for example, if the stimulus given is a boat, and for the answers from which the participant is supposed to choose is given as rabbit and boat, he is expected to say "boat". In the second subset, the participant is expected to say the object that matches the color of the stimulus and avoid naming the shape. The last subset involves playing the first and the second subset together. Pattern comparison Processing speed test- This test involves the participant to say the yes or no depending on the pictures provided look the same or not. The similarity of shapes of objects, colors are provided as stimulus. This test evaluates the processing speed of cognitive functioning.

Aim 2: Physical Activity (PA) Level

For In-Person Assessment (Group 1, 2 & 3)

Physical activity will be monitored using a wearable device or a smartphone to track the number of steps performed weekly pre and post the intervention. Participants will also be asked to visit the lab bi-weekly to upload their data upload.

Questionnaires such as **Physical Activity Scale for elderly** will be self-reported by the participant. Also, number of steps per session will be assessed using participants smartphone. For participants who have iPhones with IOS platform we shall use the "Health" application, and data will be retrieved in excel format by the use of "Qs access" application. For participants with Android phones, the "Google Fit" application will be downloaded on the phone, and data retrieved in excel format from participants' google account through the website "https://takeout.google.com/". Participants will be educated on how to email their data. Participants will be provided with a step-by-step upload

information sheet for iPhone and Android and be guided by the remote research personnel if needed any further help. All these applications are free of charge to participants and researchers. Additionally, a wearable sensor (Fitbit) would be mailed to them to their address and the physical activity (# of steps) will be recorded during the training sessions.

The Fitbit Sensor can track steps (walking & running), distance (km & miles), calories burned, exercise time and heart rate. It also stores up to 30 days of daily activity records. There is no risk involved in using Fitbit sensor as a physical activity monitor. Once they receive the sensor, they would be asked to wear it around their wrist and charge the sensor as required. After the completion of the study they would be required to mail back the sensor provided to them. A self-addressed stamped envelope will be provided to the participants to accomplish sending the same

Quality of Life: This will be assessed using the SF-36 questionnaires. Social community interactions will be assessed by the Community Integration questionnaires, The Physical Activity Scale for the Elderly will assess self-reported engagement in PA and the Geriatric Depression Scale will assess depression levels.

Motivation – Motivation index found to correlate highly with compliance will be evaluated by the 37 item self-report Intrinsic Motivational Inventory (Measures participants' Interest/Enjoyment of a target activity, and their Perceived-Competence, - Effort, and the activity's Value/Usefulness. These measures will be obtained after the intervention is completed.

AIM 3: Magnetic Resonance Imaging (MRI):

For participants interested in in-person assessment and (Groups 1 & 2) who are willing to be present in-person for the MRI scanning. The participants from both the intervention groups (A and B) willing to undergo MRI scanning will be invited to UIC center for Magnetic Resonance Research for fMRI scanning center located at [name]. Image acquisition will be performed in a 3T and 1.5T Magnetic resonance scanner (MR 750, GE healthcare, Milwaukee). A part of the research group [name] [name] will perform the work for scanning the participants for fMRI.

During the functional MRI (fMRI) session, the following protocol will be followed for assessing the changes in the structural and functional connectivity pre- to post-intervention. Prior to the MRI scanning session, the entire protocol will be administered for familiarization of the protocol to be followed in the scanner. The participant is aware of the cognitive task and instructions will be provided again once he is in the scanner. The participant will be made to practice clicking the yes and no button for responding

during the fMRI protocol. A resting period of 8 minutes prior to the imaging process will be provided so that the person is relaxed and has got adjusted to the environment.

1) Rest for 8 secs. 2) Auditory clock test- The participant will hear times of day. His/her task is to respond by clicking yes button if both the hour and minute hands are on the same side of the clock face and click no, if the hands are not on the same side of the clock face. 3) Rest. 4) Action observation- The participant will observe a Wii-fit Game in the screen. 5) Rest 6) Mental Imagery with eyes open- The participant will be instructed to imagine that they are playing the game while a scene from the Wii-fit game is projected in front. 7) Rest. 8) Action observation and mental imagery- The participant will be asked to observe a video of a Wii-fit game and will be instructed to imagine that they are playing the game. 9) Rest. 10) The participant will be instructed to close his eyes and imagine that they are performing the game observed before. 11) Rest. 12) The participant will be instructed to observe the game while he simultaneously responds to the auditory clock test. 13) Rest. 14) The participant will be instructed to observe and imagine playing the game projected while he simultaneously responds to the auditory clock test. 15) Rest.

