3.0 Objectives/Aims

Aim 1: To test the feasibility (compliance and effectiveness) of cognitive-motor exergaming (CogXergaming) in the frail older adults and to compare the improvements in behavioral biomarkers in this group across balance, muscle fitness, cardiovascular fitness and global cognition to the group receiving the Matter of Balance training.

Hypothesis: Participants will respond well to CogXergaming training paradigm and demonstrate significant improvements in balance, muscular fitness, cardiovascular fitness and global cognition as compared to the Matter of Balance training group.

Aim 2: To examine the effect of CogXergaming on physical activity levels and quality of life measures post-intervention.

Hypothesis: The participants who received CogXergaming will demonstrate significant improvement in physical activity and quality of life post-training as compared to their own pre-training scores.

Aim 3: To examine the effect of CogXergaming structural and functional connectivity within the cognitive-motor areas pre and post training to establish effect size.

Hypothesis: Post-training, participants will demonstrate improved memory consolidation, attention, motor planning and execution compared to pre-training indicating improved functional connectivity within the cognitive-motor areas.

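### The Aim 2 step outcome is a weekly total with no wear or valid-day rule, so a change in device wear reads as a change in physical activity

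*Combined protocol and SAP*

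**What the plan says.** Section 6.4 (Aim 2: Physical Activity Level) states that "Physical activity will be monitored using a wearable device or a smartphone" in order to "track the number of steps performed weekly pre and post the intervention". Of the wrist sensor it says that "they would be asked to wear it around their wrist and charge the sensor as required", and that "It also stores up to 30 days of daily activity records". The same section names two further step measures. For the phone, "number of steps per session will be assessed using participants smartphone". For the wrist sensor, "the physical activity (# of steps) will be recorded during the training sessions".

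The Aim 2 hypothesis in section 3.0 expects CogXergaming participants to show "significant improvement in physical activity and quality of life post-training as compared to their own pre-training scores".

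Section 8.0 plans general checks for outliers and entry errors. Section 12.0 plans ANCOVA for balance, cognitive, gait and cardiovascular measures; it does not list physical activity and gives no missing-data rule. None of these sections gives hours of wear per day, a minimum number of days, a way to detect non-wear, an instruction to carry the phone, or a rule for days without data.

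**The concern.** Steps are recorded only while the sensor is worn and charged or the phone is carried. A weekly total therefore depends on two things, how much the person walked and on how many days the device could see it. The plan has no rule to separate them.

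The hypothesis is judged within person, before against after training, so a general drift in wear goes straight into the estimated change. Drift could run either way. Novelty may fade and lower wear, or regular contact with staff may raise it. The first could hide a real gain and the second could create one. Of the step measures named, only the weekly count has a pre-training value, so the per-session counts cannot stand in for it.

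**Working it through.** **Inputs from the documents.** Enrolment 120 (section 5.0), attrition 20%, and 96 analysed in six subgroups of 16 (section 12.0). These reproduce: 120 × (1 - 0.20) = 96 and 96 / 6 = 16, so three CogXergaming subgroups give 3 × 16 = 48. No step mean, SD, alpha or wear rate is stated, so no figure for the step outcome itself can be reproduced.

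**Step 1. Weekly total.** Let *d* be the observed days in the week, *s* the mean steps per observed day, and *g* the true proportional change in *s*. An unadjusted weekly count is *d* × *s*, so

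apparent change = (d_post / d_pre) × (1 + g) - 1.

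The observed days below are assumed values from 5 to 7:

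| Observed days, pre to post | Ratio | Apparent change, g = 0 | Apparent change, g = +20% |
|---|---|---|---|
| 7 to 6 | 0.857 | -14.3% | +2.9% |
| 7 to 5 | 0.714 | -28.6% | -14.3% |
| 6 to 7 | 1.167 | +16.7% | +40.0% |
| 5 to 7 | 1.400 | +40.0% | +68.0% |

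**Step 2. Mean steps per valid day.** The factor *d* drops out and the apparent change equals *g*, provided that the observed days are representative of all days.

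**Step 3. Size against sampling error (illustration only).** Assume 48 participants, a two-sided 0.05 test of the within-group change, no true change, and an SD of change of 0.2 to 0.5 of mean weekly steps. A mean wear shift of half a day is 0.5 / 7 = 0.071 of the mean.
- SD 0.2: SE = 0.2 / √48 = 0.029, and the chance of a significant false change is about 70%.
- SD 0.5: SE = 0.5 / √48 = 0.072, and the chance is about 17%.

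The nominal rate is 5%.

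**Step 4. Participants lost to a minimum of 4 valid days in 7.** Assume independent days.
- Daily chance of wear 0.90 in one window and 0.75 in the other: P(at least 4 of 7) is 0.997 and 0.929. The product is 0.927, so about 7% are lost.
- Daily chance 0.85 in both windows: 0.988 × 0.988 = 0.976, so about 2% are lost.

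**Step 5. If wear depends on activity.** Step 2 fails when people leave the device off on quiet days. Assume that the log-odds of wear rise by 1.0 to 1.5 per SD of daily log steps (day-to-day log SD 0.35), and that the chance of wear on a typical-activity day goes from 0.90 to 0.75. Simulation with no true change then gives:
- mean steps per valid day: a false rise of about 4-5%;
- weekly total: a false fall of about 14%;
- participants failing the 4-day minimum: 12-16%.

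Most of that extra loss arises because overall wear is lower in this setting.

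**The case against.** The strongest reply is that the protocol is silent rather than wrong. A reader might infer that it scores unworn days as zero. It does not say so. The sentence in section 6.4 describes monitoring and is not a full variable definition, and since daily records are stored, averaging over observed days is not ruled out. That stands. What can be said is that the only stated unit is a weekly number of steps, and that a day without data adds nothing to such a number unless a rule says otherwise.

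A reader might also infer that the step windows are the assessment weeks (weeks 1 and 8 for CogXergaming, weeks 1 and 10 for Matter of Balance). Section 6.4 does not place them there, so nothing here rests on the length of the gap.

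Nor do the documents show that wear will change. With stable wear the weekly change has extra noise but no drift from wear.

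Feasibility is a fair objection. The documents say the sensor can track heart rate but describe no export of within-day data, and they tie its step recording to training sessions, so sensor data may not exist for the pre-training window. For phones, a quiet day and a phone left on a table look alike. A fixed hours-of-wear rule based on heart rate may therefore not be workable, and the definition has to follow what is retrieved.

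Finally, this is a pilot. The Physical Activity Scale for the Elderly and the SF-36 also serve Aim 2 and do not depend on wear. That limits the weight of the point but does not repair the step outcome.

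**Conclusion.** The point holds as a weakness in the stated metric. With no wear or valid-day rule, a weekly total cannot separate wear from activity, and the within-person comparison does not remove the difference. One observed day lost from seven is worth -14%, two are worth -29%, and one gained on six is worth +17%. These figures need only the assumption that unobserved days add nothing. The false-positive illustration and the loss figures rest on assumed SDs and wear rates that the documents do not give.

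Two stronger conclusions are not supported. The documents do not show that the step result will be biased, or in which direction. Steps per valid day is also not free of bias: it is unaffected by the number of days worn only if wear is unrelated to that day's activity. Under the dependence assumed in the working it is still closer to the truth than the weekly total.

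**What to change.** In section 6.4, replace the weekly total with mean steps per valid day, from the same device in the pre and post windows, and prespecify:

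- the start and length of each window;
- a valid-day definition that the retrieved data can support, for example worn hours where the sensor data are exported, and for phones, days with recorded data, with phone results reported separately;
- a minimum number of valid days in each window, for example 4 of 7, and how a window below it is handled;
- a table of valid days by arm and window, so that a shift in wear can be seen.

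The thresholds are examples, to be settled once it is known what the devices export. Section 12.0 should also name the analysis of this outcome.

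The change adds no visits and does not alter the 120 enrolled or 96 analysed. It does require that the chosen device is in use before training starts. The cost is some missing outcomes: about 2-7% under the independent-wear assumptions, and more if wear is lower or falls off on quiet days. Some bias remains if non-wear is related to activity.
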